15.3. Appendix 3: Assessment Windows

15.3.1. Definitions of Assessment Windows for Analyses

The data is analyzed as per the planned visit assignment.

Exit/withdrawal and unscheduled visits will be slotted to the appropriate planned visit. The assigned visit is based on the interval in which the Study Day for the exit/withdrawal or unscheduled visit falls according to intervals (inclusive) provided below. For completeness, the table also includes visits which are not slotted; these visits will have 'na' for 'not available' listed for the Interval Start and End Day.

| Analysis Set / Domain | Parameter (if applicable) | Target ¹ | Analysis Window | | Analysis Timepoint Number ⁴ | Analysis Timepoint |
|---------------------------------------|---------------------------|---------------------|---------------------|---------------------------|--|--------------------|
| | | | Beginning Timepoint | Ending Timepoint | | |
| All | All | NA | NA | NA | 10 | Screening |
| Year 1 Treatment Phase visits: | | | | | | |
| All | All | 1 | NA | NA | 20 | Baseline |
| | | 29 | 2 | 35 | 30 | Week 4 |
| | | 43 | 36 | 49 | 40 | Week 6 |
| | | 57 | 50 | 70 | 50 | Week 8 |
| | | 85 | 71 | 98 | 60 | Week 12 |
| | | 113 | 99 | 126 | 70 | Week 16 |
| | | 141 | 127 | 154 | 80 | Week 20 |
| | | 169 | 155 | 175 | 90 | Week 24 |
| | | 183 | 176 | 189 | 100 | Week 26 |
| | | 197 | 190 | 210 | 110 | Week 28 |
| | | 225 | 211 | 238 | 120 | Week 32 |
| | | 253 | 239 | 266 | 130 | Week 36 |
| | | 281 | 267 | 294 | 140 | Week 40 |
| | | 309 | 295 | 322 | 150 | Week 44 |
| | | 337 | 323 | 350 | 160 | Week 48 |
| 365 | 351 | 392 | 170 | Week 52 | | |
| 365 | na | Na | 175 | Survival-W52 ² | | |
| Year 2 Phase Visits: | | | | | | |
| All | All | 421 | 393 | 434 | 180 | Week 60 |
| | | 449 | 435 | 476 | 190 | Week 64 |
| | | 505 | 477 | 532 | 200 | Week 72 |
| | | 561 | 533 | 588 | 210 | Week 80 |
| | | 617 | 589 | 644 | 220 | Week 88 |
| | | 673 | 645 | 700 | 230 | Week 96 |
| | | 729 | 701 | 742 | 240 | Week 104 |

| Analysis Set / Domain | Parameter (if applicable) | Target ¹ | Analysis Window | | Analysis Timepoint Number ⁴ | Analysis Timepoint |
|-----------------------|---------------------------|---------------------|---------------------|------------------|--|----------------------------|
| | | | Beginning Timepoint | Ending Timepoint | | |
| | | 729 | na | na | 245 | Survival-W104 ² |
| | | Na | na | na | 250 | Follow-Up ³ |

NOTES:

¹ Study Day with Baseline/Treatment Start Date as Day 1. Baseline record will be derived in each analysis dataset, analysis visit number will be 15.

² Survival visit for subjects who withdraw from the double-blind treatment phase but consent to the Week 52 and Week 104 survival assessments.

³ The follow-up visit occurs 8 weeks after last dose of belimumab for subjects who discontinue study treatment and withdraw from the study up to (i) Week 52 in Arms A and B or (ii) Week 104 in Arm C.

⁴ If there are multiple visits within a visit window, the visit closest to the target date will be used. If there are two visits equidistant from the target date, then the scheduled visit will be given preference, if both are unscheduled then the first assessment will be used.

15.4. Appendix 4: Study Phases and Treatment Emergent Adverse Events

15.4.1. Study Phases for Concomitant Medication

| Study Phase | Definition |
|-------------|---|
| Prior | If medication end date is not missing and is before the first exposure date to study treatment |
| Concomitant | Any medication that is not a prior. Note that medications with partial or missing start and/or stop dates will be assumed to be concomitant unless there is evidence through comparison of partial dates to suggest otherwise |

15.4.2. Treatment Emergent Flag for Adverse Events

| Flag | Definition |
|--------------------|--|
| Treatment Emergent | 
 If AE onset date is on or after treatment start date, having been absent pre-treatment, or that worsens relative to the pre-treatment state. |

15.5. Appendix 5: Data Display Standards & Handling Conventions

15.5.1. Reporting Process

| | |
|---|------------------------|
| Software | |
| 
 The currently supported versions of SAS software will be used. | |
| Reporting Area | |
| HARP Server | : us1salx00259 |
| HARP Compound | : gsk1550188 |
| Study location | : gsk1550188\mid205646 |
| Analysis Datasets | |
| 
 Analysis datasets will be created according to CDISC standards (SDTM IG Version 3.2 & ADaM IG Version 1.0). | |
| Generation of RTF Files | |
| 
 RTF files will be generated for all reporting efforts. | |

15.5.2. Reporting Standards

| | |
|--|--|
| General | |
| 
 The current GSK Integrated Data Standards Library (IDSL) will be applied for reporting, unless otherwise stated IDSL Standards Location: https://spope.gsk.com/sites/IDSLLibrary/SitePages/Home.aspx: 
 4.03 to 4.23: General Principles 5.01 to 5.08: Principles Related to Data Listings 6.01 to 6.11: Principles Related to Summary Tables 7.01 to 7.13: Principles Related to Graphics | |
| Formats | |
| 
 GSK IDSL Statistical Principles (5.03 & 6.06.3) for decimal places (DPs) will be adopted for reporting of data based on the raw data collected, unless otherwise stated. Numeric data will be reported at the precision collected on the eCRF. The reported precision from non eCRF sources will follow the IDSL statistical principles but may be adjusted to a clinically interpretable number of DPs. | |
| Planned and Actual Time | |
| 
 Reporting for tables, figures and formal statistical analyses: 
 Planned time relative to dosing will be used in figures, summaries, statistical analyses and calculation of any derived parameters, unless otherwise stated. The impact of any major deviation from the planned assessment times and/or scheduled visit days on the analyses and interpretation of the results will be assessed as appropriate. Reporting for Data Listings: 
 Planned and actual time relative to study treatment dosing will be shown in listings (Refer to IDSL Statistical Principle 5.05.1). Unscheduled or unplanned readings will be presented within the subject's listings. Visits outside the protocol defined time-windows (i.e. recorded as protocol deviations) will be included in listings but omitted from figures, summaries and statistical analyses. | |

| Unscheduled Visits | |
|---|--|
| 
 • Unscheduled visits will not be included in summary tables with the exception of certain summaries by year interval in which unscheduled visits may appear in the “anytime post baseline” category where specified e.g. worst laboratory toxicity grades. • Unscheduled visits will not be included in figures. • All unscheduled visits will be included in listings. | |
| Descriptive Summary Statistics | |
| Continuous Data | Refer to IDSL Statistical Principle 6.06.1 |
| Categorical Data | N, n, frequency, % |
| Graphical Displays | |
| 
 • Refer to IDSL Statistical Principals 7.01 to 7.13. | |

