5.7. Cut-off Date for Primary Analyses (Year 1)

For study participants continuing in the study past the Week 52 visit, the cut-off date in the Year 1 analysis dataset will be the date of the Week 52 visit.

For participants who discontinue from the study prior to the Week 52 visit, the exit/withdrawal visit will be assigned to an assessment window as defined in [Section 15.3](#). Exit/withdrawal visit assigned to week 52 or earlier will be included in the week 52 report; exit/withdrawal visits assigned to an assessment window from Week 60 or later, will be reported in the Week 104 analysis.

Participants who withdraw at or prior to the Week 52 visit will have their follow-up visit included in the Year 1 reporting if the follow-up visit is prior to or on the day of the last subject's Week 52 visit. Follow-up visits that occur after the last subjects' Week 52

assessment will be reported in the Year 2 reporting. Hence subjects who withdraw at or prior to Week 52 will have a cut-off date that is the earliest of their week follow-up date and the last subject's Week 52 date.

Displays for the primary analysis reporting effort will include all data collected up to and including the Year 1 cut-off date for each participant. This includes adverse events and concomitant medications with a start date less than or equal to the cut-off date.

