5.9. Study Withdrawal

Study withdrawal (referred to in the protocol as dropout), is the combination of subjects who withdraw, are lost to follow-up (LTFU), or die during the study

Study withdrawal is defined as any subject who withdraws from the study prior to the analysis visit of interest (e.g. Week 52, Week 64, Week 104) and does not have a visit within ± 28 days of the target analysis visit date (excluding follow up visits).

This rule is applied consistently across all efficacy endpoints. The assessment of whether or not a subject had a visit within the ± 28 day of an analysis visit (e.g. Week 52) is performed at the domain level [e.g., a subject who had visit within 28 days for SLEDAI-2K but not a SLICC ACR assessment would be assessed on their observed data for SLEDAI-2K but would be considered withdrawn (non-responder) in SLICC ACR assessment].

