15.6. Appendix 6: Derived and Transformed Data

15.6.1. General

| |
|--|
| 
Multiple Measurements at One Analysis Time Point
 
 For continuous data, the mean of the measurements will be calculated and used in any derivation of summary statistics but if listed, all data will be presented. For continuous data, if there are two values within a time window (as per Section 15.3.1) the value closest to the target day for that window will be used. If values are the same distance from the target, then the scheduled assessment will be used, if both assessments are also unscheduled then the 1st assessment will be taken. For categorical data, if there are two values within a time window (as per Section 15.3.1) the value closest to the target day for that window will be used. If values are the same distance from the target, then the value prior to the target day will be taken. Participants having both High and Low values for Normal Ranges at any post-baseline visit for safety parameters will be counted in both the High and Low categories of “Any visit post-baseline” row of related summary tables. |
| 
Study Day
 
 Calculated as the number of days from First Dose Date: 
 Ref Date = Missing → Study Day = Missing Ref Date < First Dose Date → Study Day = Ref Date – First Dose Date Ref Date ≥ First Dose Date → Study Day = Ref Date – (First Dose Date) + 1 |

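### SAP 15.5.2 drops out-of-window visits that 15.3.1 and 15.1.1 keep, and for withdrawers' exit visits 5.9 and 15.3.1 disagree on 15 of 57 days at each key visit

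*SAP*

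**What the plan says.** Four parts of the SAP (the Reporting and Analysis Plan) decide whether a SLEDAI-2K counts at a key visit.

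- **15.5.2, listings block:** "Visits outside the protocol defined time-windows (i.e. recorded as protocol deviations) will be included in listings but omitted from figures, summaries and statistical analyses". The protocol window is 7 days either side of target, widened to 28 days only where COVID-19 prevented the visit (Protocol Section 2, footnote a to each schedule).
- **15.5.2, preceding block, on tables, figures and formal analyses:** planned time is used, and what gets assessed is "The impact of any major deviation from the planned assessment times and/or scheduled visit days on the analyses" and on their interpretation.
- **15.3.1:** "The data is analyzed as per the planned visit assignment". Only some visits are placed by study day: "Exit/withdrawal and unscheduled visits will be slotted to the appropriate planned visit". The slots are Days 351–392 for Week 52, 435–476 for Week 64 and 701–742 for Week 104.
- **5.9:** a withdrawer counts as withdrawn at a key visit only if there is no visit within 28 days of its target date. One who has a SLEDAI-2K in that interval "would be assessed on their observed data for SLEDAI-2K".

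Section 5.7 applies the 15.3.1 slots to exit visits of participants who leave before Week 52, and adds that "exit/withdrawal visits assigned to an assessment window from Week 60 or later, will be reported in the Week 104 analysis". Section 15.1.1 lists lateness as a per-protocol exclusion only when the Week 52 visit or SLEDAI-2K is more than 28 days late. Neither addendum changes any of these rules.

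**The concern.** The primary endpoint and both major secondary endpoints are binary, and a missing blinded score counts as non-response. Whether a score is kept therefore decides responder status directly.

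First, 15.5.2 contains a sentence that removes off-window visits from the statistical analyses, while the rest of the plan keeps them. A programmer who follows it would discard valid blinded scores and could turn a responder into a non-responder.

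Second, for a withdrawer whose exit visit falls near a key visit, 5.9 says the observed score counts there, but 15.3.1 may file the same score under a neighbouring visit or under none. Two programmers could each follow the plan and derive different responders.

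**Working it through.** **The plan's own windows.** The targets follow 7 × week + 1: 7×52+1 = 365, 7×64+1 = 449, 7×104+1 = 729. Each slot starts at the midpoint between adjacent targets: (337+365)/2 = 351, (421+449)/2 = 435, (673+729)/2 = 701. The table in 15.3.1 reproduces exactly.

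**Part 1: a scheduled Week 52 visit on Day 375, not COVID-related, blinded score ≤2, no treatment failure, no withdrawal.**

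1. The protocol window is 365−7 = 358 to 365+7 = 372. Day 375 is 10 days late, so it is outside.
2. Under 15.3.1 the visit keeps its Week 52 label; no limit on distance from target is given. Table 2 in 7.1.4, row 2, makes the participant a responder.
3. Under the 15.5.2 sentence, if the visit is recorded as a deviation, the score is omitted. Unless another blinded assessment fills Week 52, row 5 of Table 2 applies: non-responder. Imputation does not rescue the score, because section 2.2 of the October 2020 addendum carries forward only the 8 laboratory items and leaves the other 16 missing.
4. Under 15.1.1 the participant stays even in the per-protocol set, since 10 is not more than 28. Excluding only visits more than 28 days late makes little sense if scores 8–28 days late had already been removed from the main analysis.

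**Part 2: exit visits of withdrawers.** The 5.9 interval is target ± 28, which is 2×28+1 = 57 days. Each slot is 42 days (for example 392−351+1) and lies wholly inside its interval, so 57−42 = 15 days disagree.

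| Key visit | 5.9 interval | 15.3.1 slot | Days in 5.9 only | Where 15.3.1 puts them |
|---|---|---|---|---|
| Week 52 | 337–393 | 351–392 | 337–350; 393 | Week 48; Week 60 |
| Week 64 | 421–477 | 435–476 | 421–434; 477 | Week 60; Week 72 |
| Week 104 | 701–757 | 701–742 | 743–757 | no slot |

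Through 5.7, a Day 393 exit visit also leaves the Week 52 report, although 5.9 counts it for Week 52.

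**Can these days arise?** The schedule includes a blinded SLEDAI-2K at the Early Withdrawal visit.

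- Up to Week 52 that visit falls 7–28 days after the last dose (Protocol 5.3). It can land on Days 337–350 if the last dose was between 337−28 = Day 309 and 350−7 = Day 343.
- In Arms A and B after Week 52 it falls 7–28 days after withdrawal. Days 421–434 need a withdrawal on Days 393–427 (421−28 to 434−7). Days 743–757 need one on Days 715–728 (743−28, up to the day before target).
- The single days 393 and 477 are hard to reach. A last dose at Week 51 (Day 358) gives at most 358+28 = Day 386, and a withdrawal on Day 448 gives at most Day 476.

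**Unit of effect.** At the target sizes one responder is 1/70 = 1.4 percentage points in Arm A and 1/140 = 0.7 in Arm B.

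**The case against.** The strongest reply is that the intent is clear. The 15.5.2 sentence sits under a listings heading and is limited to visits recorded as deviations, which depends on a deviation management plan outside these documents. Section 15.1.1 shows that moderately late visits were meant to stay in. Section 5.9 says that its rule applies across all efficacy endpoints, and 7.1.1 points to 5.9 for withdrawal. Most of this stands, and it is why the point is minor. It does not remove the defect. The sentence names statistical analyses in terms. Section 15.1.1 speaks only of late visits, not early ones. The pointer to 5.9 settles who counts as withdrawn, but not which visit record holds the exit score.

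Some stronger readings are tempting, and the documents do not support them.

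- A reader might count the slot days beyond 7 days from target as data lost under 15.5.2. The slots are for exit and unscheduled visits, while the 7-day window is for scheduled visits, so that count measures nothing.
- A reader might extend Part 2 to continuing participants seen at unscheduled visits during the pandemic. Section 5.9 covers only withdrawers, so nothing there contradicts 15.3.1. A scheduled visit moved within the 28-day COVID-19 allowance is inside the protocol window and keeps its label.
- A reader might see conflicting tie rules in "if both are unscheduled then the first assessment will be used" (15.3.1) and "If values are the same distance from the target, then the value prior to the target day will be taken" (15.6.1, categorical data). Of two equidistant unscheduled visits, the first is the one before target, so these clauses choose the same visit.
- A reader might call 5.9 a departure from Protocol 10.4.1. That is arguable: withdrawal before a key visit needs a working definition, and the protocol imputes failure where later data cannot be collected, whereas 5.9 covers people whose data were collected.

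**Conclusion.** Both parts hold, as a minor point. The 15.5.2 sentence contradicts 15.3.1, its own preceding block and 15.1.1. If programmed, it makes a non-responder of a participant whose valid blinded score was taken 8–28 days from target. For withdrawers' exit visits, 5.9 and the slots used by 5.7 and 15.3.1 disagree on 15 of 57 days at each key visit; nearly all the reachable days lie before the slot at Weeks 52 and 64 and after it at Week 104. Status changes only for a withdrawer who also has a qualifying score and no treatment failure.

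The size rests on counts that the documents do not give: how many off-target visits were recorded as deviations, and how many exit visits fell on the disputed days. The number is likely small. A reader might infer that the design power is overstated, but it is not. A pooled two-proportion calculation at 10% versus 35% with 70 and 140 participants gives 98.9%, in line with the at least 98% in Protocol 10.2. Nothing here shows that any reported result is wrong.

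**What to change.** 1. In 15.5.2, delete the omission clause for efficacy endpoints or limit it to listings, and state that 15.3.1 governs which visits are analysed.
2. Use one interval per key visit for withdrawers' exit visits, written identically in 5.7, 5.9 and 15.3.1.
3. State which rule was programmed for Week 52. The second addendum confirms that the first database lock and primary analyses are past, so show any re-derivation as a post hoc sensitivity analysis. Label changes for Weeks 64 and 104 as made after the Year 1 results.
4. Report by arm how many participants change responder status at Weeks 52, 64 and 104 under the alternative rule.

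The cost is a few lines of SAP text and a small programming change. No new data are needed.

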15.6. Appendix 6: Derived and Transformed Data

15.6.1. General

| |
|--|
| 
Multiple Measurements at One Analysis Time Point
 
 For continuous data, the mean of the measurements will be calculated and used in any derivation of summary statistics but if listed, all data will be presented. For continuous data, if there are two values within a time window (as per Section 15.3.1) the value closest to the target day for that window will be used. If values are the same distance from the target, then the scheduled assessment will be used, if both assessments are also unscheduled then the 1st assessment will be taken. For categorical data, if there are two values within a time window (as per Section 15.3.1) the value closest to the target day for that window will be used. If values are the same distance from the target, then the value prior to the target day will be taken. Participants having both High and Low values for Normal Ranges at any post-baseline visit for safety parameters will be counted in both the High and Low categories of “Any visit post-baseline” row of related summary tables. |
| 
Study Day
 
 Calculated as the number of days from First Dose Date: 
 Ref Date = Missing → Study Day = Missing Ref Date < First Dose Date → Study Day = Ref Date – First Dose Date Ref Date ≥ First Dose Date → Study Day = Ref Date – (First Dose Date) + 1 |
| 
Study Completion
 
 A participant is considered to have completed the study if he/she has completed all phases of the study, including the Week 104 Visit, as defined in the Schedule of Activities(SoA) (see Section 2 of the protocol) A participant is considered to have completed the double-blind treatment phase (Year 1) of the study if he/she has completed all 52 weeks of the double-blind treatment phase, including the Week 52 Visit, as defined in the SoA (see Section 2 of the protocol) Participants who discontinue study treatment and withdraw from the study up to Week 52 are required to complete an Early Withdrawal Visit and a Follow-up Visit; the Early Withdrawal Visit is scheduled 1 to 4 weeks after the last dose of belimumab and the Follow-up Visit is scheduled 8 weeks after the last dose of belimumab Participants in Arms A or B who withdraw from the study after Week 52 are required to complete an Early Withdrawal Visit 1-4 weeks after withdrawal from the study. Participants in Arm C who discontinue study treatment and withdraw from the study after Week 52 are required to complete an Early Withdrawal Visit and a Follow-up Visit; the Early Withdrawal Visit is scheduled 1 to 4 weeks after the last dose of belimumab and the Follow-up Visit is scheduled 8 weeks after the last dose of belimumab |
| 
Visit assessments completed late
 
In the event that a PGA, or SLE flare assessment, which may be only completed once labs have been returned to the site, is recorded later than the visit date, then an imputed date will be used. The imputed PGA / SLE flare assessment date will be the earliest date for a completed SLEDAI-2K (IBA or PI) assessment. This may be different than the earliest visit within that window. If there are no SLEDAI-2K assessment dates available then the visit date is used.
 |

15.6.2. Study Population

| |
|---|
| 
Age Derivation
 
Age on any specified day (e.g. screening, 1st dose etc.) will be derived as: If the specified day is on or after the 30th June then:
 
 • Year of specific timepoint – DOB year 
If the specified day is before the 30th June then:
 
 • (Year of specific timepoint – DOB year) -1 
(Note this assumes day and month of birth is 30 June - as this information is not collected) Age at baseline will be defined as the latest of randomization date and baseline visit date, and derived as above.
 |
| 
Treatment Compliance – Belimumab
 
 • Percent compliance will be calculated based on the formula: $\text{Percent Compliance} = 100 * (\text{Number of injections prescribed} - \text{Number of injections missed}) / \text{Number of injections prescribed}$ |
| 
Extent of Exposure – Belimumab
 
 • Number of days of exposure to belimumab will be calculated based on the formula: $\text{Duration of Exposure in Days} = \text{Last injection date} - \text{First injection date} + 7$ • Only complete dates will be used when calculating duration of exposure. First and last injection dates will be used, regardless of any missed doses. • Participants who were randomized but did not report a treatment start date will be categorised as having zero days of exposure. |
| 
Extent of Exposure – Rituximab
 
 • Dose intensity in mg will be calculated as the cumulative actual dose divided by 2. • If the total volume of an infusion is not administered, the actual dose infused for that visit will be calculated as: $\text{Actual Dose infused (mg)} = \text{Planned Dose (mg)} * \text{Percentage of volume infused}$ |
| 
On Treatment Exposure (Year 1)
 
 • Number of days of On-Treatment exposure will be calculated based on the formula: $\text{Duration of On-Treatment Exposure in Days} = \text{Year 1 on-treatment end date (see Section 5.12)} - \text{First Belimumab injection date} + 1$ • Only complete dates will be used when calculating duration of study exposure. • Participants who were randomized but did not report a treatment start date will be categorised as having zero days of exposure. |
| 
On-Study Exposure (Years 1&2 Combined)
 
 • Number of days of On-Study exposure will be calculated based on the formula: |

| On-Study Exposure (Years 1&2 Combined) |
|--|
| 
Duration of On-Study Exposure in Days = Date of study completion or withdrawal – First Belimumab injection date + 1
 
 • Only complete dates will be used when calculating duration of study exposure. • Participants who were randomized but did not report a treatment start date will be categorised as having zero days of exposure. |

| Disease Duration |
|--|
| 
When the start day is missing, impute with 01. When the start day and month is missing, impute with 01 January. This will impute the longest possible duration.
 |

